### **9.8.2 Laboratory test monitoring**

In the case of elevated aminotransferases, neutropenia, thrombocytopenia, acute renal failure, or suspicion of rhabdomyolysis, the specific follow-up actions for this abnormality should be initiated according to the appended decision chart (17.4 – General guidance for the follow-up of laboratory abnormalities).

### **9.8.3 Monitoring electrocardiogram**

The ECG of any clinical trial patient with a clearly prolonged QTc interval (QTcB/QTcF  $\geq$ 500 msec) will be reported in an expedited fashion by the centralized ECG system to the investigator and to the Sponsor.

Appropriate medical diligence by the investigator, in such an instance, includes an investigation of the cause of the QTc interval prolongation. This investigation includes clinical laboratories to determine serum potassium, calcium, and magnesium levels, as well as to obtain a PK sample at the time of discovery of the QTc interval prolongation.

### **9.8.4 Overdose information**

An overdose with the IMP is an event suspected by the investigator or spontaneously notified by the patient (not based on systematic pill count) and defined as any dose above the recommended maximal dose administered within the Clinical Trial:

- Overdose is defined as 2 or more tablets of IMP in one day (a 24-hour period)

NOTE: The circumstance (ie, accidental or intentional), amount, and time period should be clearly specified in the verbatim terminology.

### **9.8.5 General guidance for relapses (refer to [Section 10.1.3.5](#) for detailed instructions)**

Subjects/parents/guardians will be instructed to contact their investigator immediately should any neurological symptom appear. The subject must be examined as soon as possible, but within 7 days of contact as follows:

Patient should have a physical exam and a complete neurological examination with FSS/EDSS by the blinded rater.

The relevant information will be sent to the RAP for confirmation of relapse.

The RAP will determine whether a subject has experienced a protocol-defined relapse. The RAP will review, in an expedited fashion, the records of all subjects who develop new or worsening neurological symptoms. All reviews will be done based on subject examination records from the Treating Neurologist and Examining Neurologist, but without knowledge of the subject's treatment assignment.

### **9.8.6 Re-consent process**

Patients/parents/guardian may decide to discontinue study treatment or to discontinue from participation in the trial at any time. In addition, to continue study participation, patients must undergo a repeat informed consent process when they enter the open label period or when they enter the optional additional extension period for young patients. They must also re-consent each time they have a RAP-confirmed relapse in the PK run-in, and each time they have a confirmed relapse in the open-label period.

The re-consent/assent process must include discussion with the patient/parents/guardians about the alternative approaches to therapy, such as all approved therapies, that are available to him or her.

Additional re-consents may be needed as per local regulations, eg, when patients turn 18.

For a regional or national emergency declared by a governmental agency, contingency measures are included in [Section 17.7](#).

## **9.9 ACCELERATED ELIMINATION PROCESS**

Oral intake of cholestyramine or activated charcoal significantly accelerates the elimination of teriflunomide. The preferred washout medication is cholestyramine. Without using the accelerated elimination procedure, it may take years for teriflunomide plasma concentrations to reach acceptable low levels ( $\leq 0.02$   $\mu\text{g/mL}$ ) due to the long elimination half-life. All patients who complete or discontinue the study drug must undergo one of the accelerated elimination procedures described below. These procedures must be carried out at the study site by the Investigator. For patients who will continue to the commercially available drug, no accelerated elimination procedure is required.

### **Accelerated elimination procedure**

The accelerated elimination procedure must be initiated in all patients who have definitively discontinued the study medication and will not continue teriflunomide treatment after completion of the study. The recommended procedure is cholestyramine with a dose adjusted for children's weight (240 mg/kg/day (80 mg TID)). Alternatively, 50 g oral activated charcoal powder administered every 12 hours for 11 days may be used.

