#### 6.3.1 Exclusion criteria related to study methodology

- E 01. Expanded Disability Status Scale score  $> 5.5$  at screening or randomization visits.
- E 02. A relapse within 30 days prior to randomization.
- E 03. Body weight  $< 20$  kg.
- E 04. Mental condition rendering the patient or parent/guardian unable to understand the nature, scope, and possible consequences of the study.
- E 05. Patient or parent/guardian unlikely to comply with the protocol as determined by Investigator, eg, uncooperative attitude, inability to return for follow-up visits.

- E 06. Clinically relevant cardiovascular, hepatic, neurological, endocrine, or other major systemic disease making implementation or interpretation of the study results difficult or that would put the patient at risk by participating in the study.
- E 07. Persistent significant or severe infection.
- E 08. History of drug or alcohol abuse.
- E 09. Patient or parent/legal guardian is the Investigator or any Sub investigator, research assistant, pharmacist, study coordinator, other staff or relative thereof, directly involved in the conduct of the study. Any technical/administrative reason that makes it impossible to randomize the patient in the study.
- E 10. Contraindication for MRI, ie, presence of pacemaker, metallic implants in high-risk areas (ie, artificial heart valves, aneurysm/vessel clips), presence of metallic material (ie, shrapnel) in high-risk areas, known history of allergy to any contrast medium

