## **7.2 NON-INVESTIGATIONAL MEDICINAL PRODUCT(S)**

Cholestyramine or activated charcoal is used as non IMP in this study during the 4-week post elimination period to accelerate teriflunomide elimination process (see [Section 9.9](#)).

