**Table 2 - Washout medications and dosage**

	Cholestyramine	Activated Charcoal
Washout (11 days)	240mg/kg/day TID	2 x 50 g = 100 g daily

After treatment with either cholestyramine or activated charcoal taken for 11 days, the teriflunomide plasma concentration has to be verified as  $<0.02 \mu\text{g/mL}$  prior to withdrawal from/completion of the study. A post-washout PK sample will be collected immediately following administration of washout medication and at both post-drug elimination follow up visits (EOT+2W and EOT+4W). The PK samples after washout will be labeled separately from the regular pharmacokinetic samples (using labels and tubes provided in the Washout lab kit) and will be analyzed using a more sensitive bioanalytical assay (see [Section 9.11.3](#)). Feed-back on plasma levels above  $0.02 \mu\text{g/mL}$  will be provided only when requested by the Investigator, eg, in case of desired pregnancy. This is applicable for women or men wishing to parent a child, or in specific situations, including planned prescription of fingolimod, natalizumab or mitoxantrone. If the sample collected at EOT+2 weeks has blood plasma levels of teriflunomide  $>0.02 \mu\text{g/mL}$ , the site will be notified at EOT+4 weeks and the cholestyramine/charcoal treatment should be repeated. The level should continue to be followed every two weeks until it is equal or below  $0.02 \mu\text{g/mL}$ .

Both cholestyramine and activated charcoal may influence the absorption of estrogens and progestogens and reduce the effectiveness of oral contraceptives; therefore, the use of alternative contraceptive methods for women is recommended during the accelerated elimination procedure.

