#### **10.3.2.2 Handling of patients after definitive treatment discontinuation**

Patients will be followed up according to the study procedures up to the scheduled date of study completion (96 weeks from randomization), or up to recovery or stabilization of a followed-up AE, whichever comes last.

If possible, all patients who prematurely and permanently discontinue study medication will be asked to perform EOT visit procedures and will be scheduled for post drug elimination visits. Wash-out medications should be prescribed (Cholestyramine or Activated charcoal, see [Section 9.9](#)). All definitive treatment discontinuation should be recorded by the Investigator in the appropriate eCRF pages when considered as confirmed.

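### Section 9.9 of the protocol drops '/kg' from the per-dose cholestyramine amount, so the washout instruction contradicts itself for every eligible patient

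*Protocol*

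**What the plan says.** Section 9.9 of the protocol requires accelerated elimination in all patients who definitively stop study drug and will not go on taking teriflunomide. It names the drug of choice: "The preferred washout medication is cholestyramine". Under the sub-heading Accelerated elimination procedure it continues: "The recommended procedure is cholestyramine with a dose adjusted for" the child's weight. The dose follows in brackets as "240 mg/kg/day (80 mg TID", where the bracket closes.

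Table 2, in the same section, gives cholestyramine as "240mg/kg/day TID" for 11 days. It states no amount per administration.

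Other sections mention the drug without a dose and send the reader to Section 9.9:

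- Section 7.2: "Cholestyramine or activated charcoal is used as non IMP in this study during the 4-week post elimination period".
- Section 10.3.2.2: "Wash-out medications should be prescribed (Cholestyramine or Activated charcoal".

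**The concern.** Two amounts stand side by side in one dosing instruction, and they are in different units. The daily dose scales with body weight. The per-dose amount, as printed, does not. They cannot both be right for a patient who meets the entry criteria.

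This line is the working instruction for a procedure that most patients leaving treatment must undergo, and the patients are children and adolescents. A prescriber who looks for the amount to give at each administration finds one number in the protocol, and its unit is wrong. If that number were followed literally, the washout dose would be far too small.

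**Working it through.** **Inputs**

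- Daily dose: 240 mg/kg/day (protocol Section 9.9 and Table 2).
- Printed per-dose amount: 80 mg, with no '/kg' (Section 9.9).
- Frequency: TID, defined in the list of abbreviations as three times a day.
- Lowest eligible body weight: 20 kg, from exclusion criterion E 03 in Section 6.3.1.
- A second reference weight: 40 kg, the cut-off between the two study-drug dose bands (Sections 3.2.3 and 7.1.1).

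**Step 1: reproduce the per-dose figure from the daily dose.**

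Per dose = daily dose / 3 = 240 mg/kg/day / 3 = 80 mg/kg.

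The number 80 is reproduced. The printed unit is not: it should be mg/kg, not mg.

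**Step 2: read the bracket literally.**

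80 mg x 3 = 240 mg/day in total, at any body weight.

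**Step 3: compare the two readings.**

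For a patient of weight w kg, the ratio of the two daily totals is (240 x w) / 240 = w. The readings agree only at w = 1 kg.

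| Body weight | Per dose at 80 mg/kg | Per dose as printed | Daily at 240 mg/kg | Daily from the bracket | Ratio |
|---|---|---|---|---|---|
| 20 kg | 80 x 20 = 1,600 mg | 80 mg | 240 x 20 = 4,800 mg | 240 mg | 20 |
| 40 kg | 80 x 40 = 3,200 mg | 80 mg | 240 x 40 = 9,600 mg | 240 mg | 40 |

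Since no one under 20 kg may enter, the two figures disagree at least 20-fold for every patient at entry.

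**Step 4: decide which reading is intended.**

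Three things point to 80 mg/kg. The sentence says that the dose is adjusted for weight. The quotient 240/3 is exactly 80. Table 2 repeats the per-kilogram daily dose with the same frequency. Neither document gives a flat 80 mg dose elsewhere or explains one.

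**Step 5: rule out a text-extraction fault.**

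The line is running prose in the current protocol, not a broken table or a redaction. The '/kg' survives in the daily dose immediately before the bracket and again in Table 2.

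**The case against.** The strongest reply is that this is an obvious slip which a careful reader repairs at once. The bracket sits inside a phrase about weight-adjusted dosing, directly after a mg/kg figure, so the natural reading is that the unit carries over. Table 2 states the drug, the per-kilogram daily dose, the frequency and the duration; a prescriber can work from it alone and divide by three. The 20-fold and 40-fold ratios are simply body weight, and they arise only if the bracket is read in isolation.

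There are safeguards too. Section 9.9 has the Investigator carry out the procedure at the site. After the 11 days, "the teriflunomide plasma concentration has to be verified as" below 0.02 µg/mL. A level above that at EOT+2W leads to site notification at EOT+4W and a repeat course, with levels then followed every two weeks.

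Most of this stands, and it limits the risk of an actual dosing error. It does not make the printed line correct. Table 2 gives no per-dose amount, and nothing in the text says that the table prevails. The plasma checks find a failed washout afterwards and do not prevent a misread dose. It is also fair to call this a unit error rather than an arithmetical one, since the number itself is right.

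**Conclusion.** The concern holds. The per-dose amount in Section 9.9 lacks '/kg' and contradicts the daily dose printed beside it for every eligible patient, by a factor equal to body weight in kilograms and so at least 20 at entry. That factor is the size of the contradiction on the page, not a forecast of under-dosing.

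The conclusion rests on TID meaning three equal doses and on the per-kilogram daily dose being the intended one. Table 2 and the weight-adjustment wording both support the latter, but the sponsor should confirm it. No delay to washout and no consequence for contraception or blinding is claimed. The point has no bearing on power, type I error or any efficacy analysis. It merits correction because it is an operative paediatric dosing line and the only per-dose cholestyramine amount in the documents.

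**What to change.** Once the sponsor has confirmed the intended dose, change the bracket in Section 9.9 so that the regimen reads 240 mg/kg/day (80 mg/kg TID) for 11 days. As an optional consistency step, add the 80 mg/kg per-dose amount to the cholestyramine cell of Table 2, which already has the correct daily dose and duration.

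The cost is one unit in one sentence, plus one added figure if the table is also changed. Nothing in the design, sample size or analysis has to move.

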**Table 2 - Washout medications and dosage**

	Cholestyramine	Activated Charcoal
Washout (11 days)	240mg/kg/day TID	2 x 50 g = 100 g daily

After treatment with either cholestyramine or activated charcoal taken for 11 days, the teriflunomide plasma concentration has to be verified as  $<0.02 \mu\text{g/mL}$  prior to withdrawal from/completion of the study. A post-washout PK sample will be collected immediately following administration of washout medication and at both post-drug elimination follow up visits (EOT+2W and EOT+4W). The PK samples after washout will be labeled separately from the regular pharmacokinetic samples (using labels and tubes provided in the Washout lab kit) and will be analyzed using a more sensitive bioanalytical assay (see [Section 9.11.3](#)). Feed-back on plasma levels above  $0.02 \mu\text{g/mL}$  will be provided only when requested by the Investigator, eg, in case of desired pregnancy. This is applicable for women or men wishing to parent a child, or in specific situations, including planned prescription of fingolimod, natalizumab or mitoxantrone. If the sample collected at EOT+2 weeks has blood plasma levels of teriflunomide  $>0.02 \mu\text{g/mL}$ , the site will be notified at EOT+4 weeks and the cholestyramine/charcoal treatment should be repeated. The level should continue to be followed every two weeks until it is equal or below  $0.02 \mu\text{g/mL}$ .

Both cholestyramine and activated charcoal may influence the absorption of estrogens and progestogens and reduce the effectiveness of oral contraceptives; therefore, the use of alternative contraceptive methods for women is recommended during the accelerated elimination procedure.

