### **7.3.1 Measures to protect blinding of this trial**

Please also refer to [Section 7.3.2](#) randomization code breaking during the study. In the case of an SAE, the Investigator may only break the code in exceptional circumstances when knowledge of the IMP is essential for treating the patient. The treatment codes will be unblinded by the Pharmacovigilance Department for reporting of any unexpected SAE that is reasonably associated with the use of IMP. A list of expected events commonly associated (and therefore not unexpected) for teriflunomide can be found in the current Investigator Brochure (IB).

The DMC will review unblinded data. An independent statistical group (ISG), completely independent from the Sponsor and Investigators, is responsible for performing the interim data analyses and preparing the interim report for the DMC.

The laboratory responsible for the pharmacokinetic sample bioanalysis will be unblinded as well as the pharmacometrician who will calculate the individual predicted PK parameters during the PK run-in. They will, however, agree to follow the procedures defined in the Sanofi SOP/Quality documents to maintain the blind and not to disclose the randomization schedule or the individual unblinded analytical results before the database lock.

Post accelerated elimination PK samples, collected at the post accelerated elimination follow up visits (EOT+2 and EOT+4) to verify plasma teriflunomide concentrations of  $\leq 0.02 \mu\text{g/mL}$ , could potentially unblind the investigational site to a patient's treatment after study medication discontinuation. Site notification is required to inform the Investigator if the accelerated elimination procedure needs to be repeated after EOT+4 if the teriflunomide plasma concentration at EOT+2 is still above threshold. The risk of unblinding (of discontinued or completed patients) is low, since greater than 97% of the patients treated with teriflunomide are expected to have

adequately low plasma teriflunomide concentrations following the recommended accelerated elimination procedure.

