#### **10.1.4 Post drug elimination follow up visits**

Two post-washout follow up visits should be scheduled 2 weeks and 4 weeks after study medication discontinuation and initiation of the washout procedure. These visits are not required in case the patient receives commercial product immediately after the study end.

The following items will be checked/performed and recorded at Visit 21 (EOT+2W) and Visit 22 (EOT+4W):

- Adverse events reporting.
- Concomitant medications.
- Vital signs (BP, HR, body temperature and weight).
- Physical examination at EOT + 2 Weeks only.
- ECG should be performed only for patients who had new abnormalities on the EOT ECG.
- Clinical safety laboratories
  - Hematology and differential panel,
  - Liver function panel,
  - Pancreatic enzyme tests,
  - Uric acid and inorganic phosphorus.
- Post-washout PK sampling (note that the EOT+4W PK sample should be taken even if the EOT+2W PK sample is under 0.02 µg/mL, to document stability level as per EU SmPC).

In case of adverse events AE/abnormal laboratory values, or teriflunomide level > 0.02 µg/mL after the elimination treatment, follow up until resolution should be planned.

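### A post-washout level that is low at EOT+2W but above 0.02 µg/mL at EOT+4W is not automatically reported to the site, although Protocol 10.1.4 requires follow-up of it

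*Protocol*

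**What the plan says.** Protocol 9.9 (text under Table 2) sets the reporting rules.

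- The level must be verified as low "prior to withdrawal from/completion of the study".
- Samples are taken immediately after the washout and at both follow-up visits, EOT+2W and EOT+4W.
- By default, feed-back on levels above 0.02 µg/mL "will be provided only when requested by the Investigator". The reasons given include a wish to have a child and a planned switch to certain other MS drugs.
- The exception is an EOT+2W sample above the threshold. In that case "the site will be notified at EOT+4 weeks and the cholestyramine/charcoal treatment should be repeated". It goes on: "The level should continue to be followed every two weeks until it is equal or below" 0.02 µg/mL.

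Protocol 7.3.1 repeats the same trigger from the blinding side. The site is told that washout must be repeated "if the teriflunomide plasma concentration at EOT+2 is still above threshold".

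Protocol 10.1.4 sets the duties at the follow-up visits.

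- It notes that "the EOT+4W PK sample should be taken even if the EOT+2W PK sample is under" 0.02 µg/mL, and gives the reason: "to document stability level as per EU SmPC".
- For a level above 0.02 µg/mL "after the elimination treatment, follow up until resolution should be planned". This duty is not restricted to the EOT+2W sample.

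**The concern.** The EOT+4W sample is there to show that a low level stays low. The result that matters most from it is a raised value after a low EOT+2W value, and this is the result for which no alert is written. Section 10.1.4 gives the site a duty that starts with that result, while 9.9 says the result is not sent unless requested.

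Silence could also mislead. A site is told at EOT+4W if the EOT+2W level was raised, so hearing nothing implies that EOT+2W was low. An investigator could take that to mean elimination is complete and have no prompt to ask about the later sample.

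At stake is a delay or omission of the repeat washout and the extended follow-up. Section 9.9 says that, without accelerated elimination, low levels may take years to reach. Section 3.1.2.2 reports embryofetal toxicity in rats and rabbits, and the trial enrols adolescents.

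**Working it through.** No sample size, power or event count is involved, so there is no planned figure to reproduce. The check sets the rules side by side and follows each combination of the two follow-up results.

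**Inputs**

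- Default reporting rule: on request (9.9).
- Automatic trigger: EOT+2W above 0.02 µg/mL (9.9 and 7.3.1).
- EOT+4W sample mandatory even if EOT+2W is low (10.1.4).
- Follow-up until resolution if the level is above 0.02 µg/mL (10.1.4).
- Verification before leaving the study (9.9).

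**Result combinations under the written rules**

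| EOT+2W | EOT+4W | Automatic notice to site | Follow-up required by 10.1.4 |
|---|---|---|---|
| low | low | none needed | no |
| high | low | yes (9.9, 7.3.1) | yes, for the EOT+2W level |
| high | high | yes (9.9, 7.3.1) | yes |
| low | high | **none; on request only** | **yes** |

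The last row is the gap. The sample taken immediately after washout does not close it, because no automatic notice is attached to that sample either.

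**Timing of the two samples**

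Take the day study drug stops as day 0. Washout starts that day or the next (10.1) and lasts 11 days (9.9), so its last day is day 10 or day 11.

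- EOT+2W, nominal day 14: 14 − 11 = 3 to 14 − 10 = 4 days after washout ends.
- EOT+4W, nominal day 28: 28 − 11 = 17 to 28 − 10 = 18 days after washout ends.

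The visit window is ±7 days (flow chart 1.2, note a), so these figures are nominal only. EOT+2W can fall on days 7 to 21, that is from 7 − 11 = −4 to 21 − 10 = 11 days relative to the last washout day. At the early end the sample precedes the end of washout. EOT+4W can fall on days 21 to 35, that is from 21 − 11 = 10 to 35 − 10 = 25 days after it. The alert is thus attached to the sample nearer the washout, and the later sample, which tests stability, has none.

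**Other provisions that might deliver the result**

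- The clinical trial summary says both samples are used to verify the level and that further samples may be needed.
- Section 5.1.1 allows the 4-week follow-up to be extended until the level is at or below 0.02 µg/mL.
- Section 6.3.4 keeps double contraception in place until elimination is confirmed.

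Each of these creates a duty or a safeguard. None says that the EOT+4W value is sent to the site.

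**The case against.** The strongest reply is that the protocol already covers this patient. Verification before exit is mandatory, follow-up can be extended, contraception continues, and the investigator may ask for any result, since the listed reasons are only examples. On that reading the point is merely whether the result is sent or fetched. Much of this stands, and it is why harm is limited. It does not remove the mismatch: 9.9 does not say who verifies or how the site learns the value, and its stated default is not to send it.

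A second reply is that restricted feed-back protects the blind. Section 7.3.1 does say that post-washout samples could unblind a site. But it accepts that exposure for EOT+2W and calls the risk low. After the open-label period the argument has little force: every patient there receives teriflunomide whatever the original arm (5.1), so a raised level does not reveal the randomised assignment.

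A third reply is that an alert may be set out in the central laboratory or operational manuals cited in 9.6 and 9.11.2, which are not among the documents. That is possible. Such an alert would then go beyond the on-request rule in 9.9, and the protocol text would still need to agree with it.

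A reader might also infer that no later contact could reveal a missed result, because the SAP (2.1.4) names EOT+4W as the last planned open-label visit. The documents do not support that. The SAP passage defines an observation period for analysis, not a limit on conduct, and Protocol 5.1.1 allows follow-up to run longer.

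**Conclusion.** The point holds as a gap in written procedure. For a patient low at EOT+2W and raised at EOT+4W, 10.1.4 requires follow-up, but 9.9 and 7.3.1 give the site the triggering result only if it asks. This is a worthwhile, inexpensive improvement. It does not show that patients are left unprotected.

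The case is probably rare, but its size cannot be given as a number because the documents state no rate for a rise between the two samples. Two tempting figures should not be used.

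- A reader might conclude from the more than 97% success expected in 7.3.1 that fewer than 3% of patients could be affected. That section names no sampling time, so a patient who is low at EOT+2W and raised later could already count among the successes.
- A reader might treat the table above as showing the share of raised results that is covered. It lists combinations without probabilities and says nothing about how many patients fall in each.

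The conclusion assumes that no reporting rule outside the two documents overrides 9.9.

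**What to change.** In 9.9, widen the notification sentence so that it applies when either the EOT+2W or the EOT+4W sample is above 0.02 µg/mL. The site is notified, washout is repeated, and levels are checked every two weeks until at or below 0.02 µg/mL. For a raised EOT+4W sample, notify as soon as the result is available. Make the matching change in 7.3.1 so that the blinding section names both samples.

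The cost is a few words in each of two sentences and one further alert from the laboratory. No scheduled sample or visit is added; repeat washout and extra levels fall only on patients whom 10.1.4 already says to follow. The downside is a small added unblinding exposure for patients washed out after double-blind treatment.
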